3.4.3 Estimation of MTD/RP2D

A 2-parameter BLRM employing the escalation with EWOC principle will be used during the escalation phase for selection of doses to investigate and for estimation of the MTD (Section 9.3.4.1). The general plan is that cohorts of subjects will receive escalating doses of AFM24 until the MTD is reached. Each cohort will consist of newly enrolled subjects.

Estimation of the MTD during the escalation phase of the study will be based upon the estimation of the probability of DLT in Cycle 1 in subjects who are evaluable for DLT assessment. If the MTD cannot be reached in the dose escalation phase (Phase 1), one or more RP2Ds will be determined as the dose resulting in the best therapeutic window for AFM24 based on the review of DLTs, AEs, serious AEs (SAEs), and laboratory, PK, and PD data. MTD and/or at least one RP2D (as defined in Section 3.4.3) might be determined based on dosing schedules and cancer indications.

At all decision time points, the adaptive BLRM permits alterations in the dose increments based on the observed toxicities. It will be possible for additional, intermediate dose levels to be added during the study.

Dose escalation will not exceed a 200% increase from the current dose being studied. Cohorts may be expanded at any dose level below the highest dose deemed unacceptable in order to better understand safety, tolerability, PK, or PD.

Provisional dose escalation levels are provided in Table 4; however, dose decisions during escalation are not limited to the values provided. Based on the recommendation of the BLRM regarding the highest dose that may not be exceeded at any decision point during escalation and the maximum increase in dose allowed by the protocol, intermediate doses may be administered to subsequent new cohorts of subjects. This includes doses lower than the starting dose or intermediate doses between the current and next (lower or higher) provisional doses. To further characterize the safety, PK, and/or PD, for a dose of AFM24 that is considered acceptably safe, i.e., lower than the MTD, the associated cohort may be expanded. In addition, dose escalation may be terminated at any time without establishing the MTD based on emerging safety concerns or based on clinical and laboratory data that indicate an optimal biologically active dose has been reached.

Table 4: Provisional Dose-Escalation Levels

Dose Level	Proposed Dose ^a (mg)	Increment from previous dose
-1 ^b	7	50% decrease
1	14	Starting dose
2	40	200%
3	120	200%
4	360	200%
5	1000	200%

- a. It is possible for additional, intermediate dose levels to be added during the course of the study.
- b. Dose level -1 represents a dose that may be evaluated if dose level 1 is poorly tolerated. No dose de-escalation below this level is planned for this study. If dose level -1 is poorly tolerated the study will be terminated.

3.4.4 Replacement of Subjects

In the first 2 cohorts of the dose escalation phase (Phase 1) a subject will be replaced (ie, an additional subject will be added to the cohort) if only 1 or none of the treated subjects is evaluable for DLT assessment.

In the subsequent cohorts a subject will be replaced (ie, an additional subject will be added to the cohort) if less than 3 subjects are evaluable for DLT assessment.

In the dose expansion phase (Phase 2a) all patients in the **safety set** will not be replaced, independent of the availability of their post-baseline disease assessments.

3.5 Dose and Schedule Modifications

The BLRM will be updated with the newly accumulated data. The overdose risk will then be calculated for each dose, and escalation will be permitted to all doses, which fulfill the EWOC criterion (Section 9.3.4.1).

If DLTs are observed in the first 2 consecutive subjects receiving a dose level that has not been cleared for safety, subsequent enrollment to that cohort will be stopped. The BLRM will be re-run to confirm that the dose-level still fulfills the EWOC criterion. Based on this information, the SRC will evaluate whether the next subjects will be enrolled on the same dose level, or if they will be enrolled to a lower dose level.

Dose decisions for dose escalation cohorts (Phase 1) and additional dosing schedules to be explored in the expansion cohorts (Phase 2a) will be based on all relevant data available including safety information, DLTs, all \geq CTCAE Grade 2 toxicity data during Cycle 1 and PD and PK data, as available, from evaluable subjects in any cohort.

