Dose Cohort 3 and any subsequent cohorts will enroll at least 3 subjects. A fourth subject may be enrolled if treatment of the fourth subject is anticipated to begin within 14 days of treatment initiation of the third subject in the cohort. The first 2 subjects of each dose cohort will begin treatment in a staggered approach with at least 7 days between first dosing of these 2 subjects. Subsequent subjects may be enrolled concurrently. All subjects who start treatment need to complete the 28-day DLT observation period or experience a DLT before the SRC meeting and dose escalation decision. A minimum of 3 subjects need to be evaluable for DLT assessment (Section 3.4.2) to allow for a dose escalation decision by the SRC. If less than 3 subjects are evaluable for DLT assessment, replacement subject(s) will be enrolled. The dose cohorts might be extended to up to 6 subjects based on the SRC decision.

The BLRM will be assessed for those subjects who are evaluable for DLT assessment in the dose-determining set (DDS) consisting of all subjects who received at least 1 dose of AFM24, and either experienced a DLT at any time during Cycle 1 or met the minimum treatment and safety evaluation requirements without experiencing a DLT within Cycle 1. After completion of a given dose cohort, or at any time the BLRM is updated, the decision to dose escalate and the actual dose chosen will be based on the recommendation of the BLRM regarding the highest admissible dose according to the EWOC principle (Section 9.3.4.1) and the medical review of all available clinical, laboratory, and PK data. The outcome of these analyses and the respective datasets will be reviewed by the SRC consisting of the Principal Investigators at each study center and the Sponsor's Medical representative(s), and additional clinical experts, as needed. The SRC will confirm the dose level selection of the next dose cohort prior to enrollment. Dose escalation will continue until the MTD and/or at least one RP2D is determined.

In the event of a Common Terminology Criteria for Adverse Events (CTCAE) Grade 5 adverse event (AE) or a second CTCAE Grade 4 AE at least possibly related to AFM24 at any time during Phase 1, the Sponsor will suspend further accrual and will perform a safety analysis that will be reviewed by an ad-hoc SRC meeting to decide on further progression of the study.

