3.6 Safety Review Committee

The SRC will consist of the Sponsor's medical representative and the Principal Investigator or delegate from each active study center. The SRC will be co-chaired by 1 of the participating Principal Investigators and the Sponsor's medical representative. The study statistician will participate in the SRC. *Ad hoc* participants such as the clinical pharmacology scientist and clinical operations leader may be invited as appropriate. Additional experts may be consulted by the SRC as needed. Appropriate representatives of the coordinating contract research organization will also attend and minute the meeting.

The SRC has the responsibility for monitoring the clinical study's progress and the safety of the participating subjects. After there are 2 evaluable subjects for the first 2 cohorts and at least 3 evaluable subjects for subsequent cohorts at each dose level during Phase 1 of the study, the SRC will review and assess all available safety data from the cohort together with available PK data and recommendations from the BLRM to make a decision on the dose for the next cohort of subjects. The decision may be to:

- Proceed with dose escalation;
- Expand the cohort to a maximum of 6 evaluable subjects;
- De-escalate the dose to a lower dose level or to an intermediate lower dose level; or
- Stop the dose escalation.

The decisions and decision-making of the SRC will be documented and will be provided to the Investigators before dosing any new subjects on the next dose level.

During the dose expansion phase (Phase 2a) of the study, an Independent Data Monitoring Committee (IDMC) will periodically review all safety data generated throughout the dose expansion phase (Phase 2a) part of the study on a regular basis ([Section 3.7](#)).

All details regarding the SRC composition, meetings, reviewed data and the decision-making process will be documented in the study-specific SRC Charter.

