14.5.1.1 Hypothetical Data Scenarios

Hypothetical data scenarios are shown in [Table 19](#). These scenarios reflect potential on-study data constellations and related escalation as allowed by the model and the 200% escalation limit. For each scenario, the probability of overdose for the current dose, as well as the next potential dose and related probabilities of under-dosing, target dose and over-dosing are shown.

For example, scenario 1 represents the case that no DLT is observed in the first subject at the starting dose of 14 mg. In this case, the next dose permitted by the model and by the 200% escalation rule is 40 mg. In scenario 5a, while no DLT was observed at dose 14 mg, 1 DLT is observed in the first 2 subjects at 40 mg and the model would then not allow to escalate and would require to stay at 40 mg and treat 4 more subjects at 40 mg before escalating to 120mg (scenario 5b). In scenario 9b, an intermediate dose escalation is shown: While no subject experienced a DLT at dose levels 14 mg and 40 mg, 1 DLT was observed at 120 mg. The model would require that in total 6 subjects are treated at 120 mg and would thereafter only allow to escalate to 200 mg (and not to the maximum of the next level, which is 360 mg), to prevent potential overdosing. These cases illustrate the adaptive behavior of the model.

Table 19: Hypothetical Data Scenarios

Scenario	Dose	Data - #DLT	Data - #Sub	CD - P(OD)	Next Dose	ND - P(UD)	ND - P(TD)	ND - P(OD)
1	14	0	2	0.014	40	0.881	0.085	0.035
2	14	1	2	0.322	7	0.500	0.251	0.249
3	14	1	3	0.207	14	0.524	0.269	0.207
4	14	0	2	0.012	120	0.788	0.135	0.076
	40	0	2					
5a	14	0	2	0.209	40	0.506	0.285	0.209
	40	1	2					
5b	14	0	2	0.041	120	0.461	0.306	0.233
	40	1	6					
6	14	1	6	0.052	120	0.486	0.317	0.197
	40	0	3					
7	14	0	2	0.603	7	0.466	0.299	0.235
	40	2	2					

Scenario	Dose	Data - #DLT	Data - #Sub	CD - P(OD)	Next Dose	ND - P(UD)	ND - P(TD)	ND - P(OD)
8	14	0	2	0.013	360	0.571	0.184	0.245
	40	0	2					
	120	0	3					
9a	14	0	2	0.159	120	0.526	0.315	0.159
	40	0	2					
	120	1	3					
9b	14	0	2	0.043	200	0.471	0.312	0.217
	40	0	2					
	120	1	6					
10	14	0	2	0.221	120	0.344	0.434	0.221
	40	0	2					
	120	2	6					
11	14	0	2	0.062	360	0.487	0.293	0.220
	40	0	2					
	120	1	6					
	200	0	3					
12	14	0	2	0.036	1000	0.585	0.190	0.225
	40	0	2					
	120	0	3					
	360	0	3					
13	14	0	2	0.280	200	0.685	0.251	0.063
	40	0	2					
	120	0	3					
	360	1	3					

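### Section 3.5's within-cohort stop looks only at the first two consecutive subjects; two DLTs in another order (at least one below Grade 4) require no model re-check before a fourth, replacement or approved expansion subject

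*Protocol*

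**What the plan says.** Protocol Section 3.5: "If DLTs are observed in the first 2 consecutive subjects receiving a dose level that has not been cleared for safety, subsequent enrollment" is halted for the cohort in question. Next, "The BLRM will be re-run to confirm that the dose-level still fulfills the EWOC criterion", and on that basis "the SRC will evaluate whether the next subjects will be enrolled on the same dose level" or on a lower one.

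The other controls that bear on an open cohort are these.

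- **Suspension by grade (Protocol 3.4, 9.3.8.1; SAP 8).** Accrual is suspended in Phase 1 for a Grade 5 event, or for a second Grade 4 event at least possibly related to AFM24. Order does not matter.
- **Scheduled SRC review (Protocol 3.6).** "After there are 2 evaluable subjects for the first 2 cohorts and at least 3 evaluable subjects for subsequent cohorts", the SRC reviews the cohort with the BLRM recommendation.
- **Fourth subject (Protocol 3.4, cohort 3 onward).** "A fourth subject may be enrolled if treatment of the fourth subject is anticipated to begin within 14 days" of the third subject's start.
- **Replacement (same section).** "If less than 3 subjects are evaluable for DLT assessment, replacement subject(s) will be enrolled".
- **Expansion.** The SRC may extend a cohort to six. Appendix E (14.5.1.1) illustrates this. After 1/2 at 40 mg the model "would require to stay at 40 mg and treat 4 more subjects at 40 mg before escalating to 120mg"; after one DLT at 120 mg, "The model would require that in total 6 subjects are treated at 120 mg".
- **EWOC (Protocol 9.3.4.1).** A dose with more than a 25% chance of a DLT rate of 33% or higher is ruled out, but the wording applies to the next cohort. The prior is updated after each cohort. Section 3.4 contemplates updates at other times and does not require them.

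The SAP adds no within-cohort DLT rule.

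**The concern.** The Section 3.5 trigger depends on which subjects had the DLTs. The model depends only on how many subjects at each dose had one. Two DLTs among three subjects can fall in three orders, and only one of them (subjects 1 and 2) fires the rule. Even if the wording is read as any two subjects in sequence, DLT / no DLT / DLT is still missed.

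The protocol already treats two DLTs at an uncleared dose as a reason to pause, re-run the model and ask the SRC. In the missed orders, another subject can be dosed at a level that the model would class as inadmissible before anyone is required to run it. The protocol's own Grade 4 rule counts events without regard to order; the DLT rule does not.

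**Working it through.** **Inputs.** From Protocol 9.3.4.1 and Table 8: logit p(d) = log α + β·log(d/180 mg), with independent normal priors on (log α, log β), means −1.983 and −0.217, SDs 2 and 1. The likelihood is binomial. Overdose risk is P(p(d) ≥ 0.33 | data), and the limit is 0.25. The posterior was integrated numerically on a 1201 × 1201 grid. Minimum cohort sizes are 2, 2, 3, 3 at 14, 40, 120 and 360 mg (Protocol 3.4).

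**Step 1: reproduce Table 19 (overdose risk at the current dose).**

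| Scenario | Data at current dose | Printed | Recomputed |
|---|---|---|---|
| 5a | 1/2 at 40 mg | 0.209 | 0.205 |
| 7 | 2/2 at 40 mg | 0.603 | 0.604 |
| 9a | 1/3 at 120 mg | 0.159 | 0.166 |
| 10 | 2/6 at 120 mg | 0.221 | 0.224 |
| 13 | 1/3 at 360 mg | 0.280 | 0.280 |

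All 15 rows of Table 19 agree within 0.01, so the model is the plan's own.

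**Step 2: overdose risk at the current dose, lower cohorts DLT-free and of minimum size.**

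| DLTs / subjects | 14 mg | 40 mg | 120 mg | 360 mg | 1000 mg |
|---|---|---|---|---|---|
| 2/2 | 0.81 | 0.60 | 0.65 | 0.89 | 0.86 |
| 2/3 | 0.65 | 0.47 | 0.51 | 0.71 | 0.69 |
| 2/4 | 0.50 | 0.36 | 0.40 | 0.55 | 0.54 |
| 2/5 | 0.375 | 0.27 | 0.30 | 0.42 | 0.42 |
| 2/6 | 0.28 | 0.20 | 0.22 | 0.32 | 0.32 |

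Under this history, two DLTs exceed 0.25 at every dose up to five subjects, even if pending subjects are counted as DLT-free.

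**Step 3: which cells can be followed by another dosing without a required check?**

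- *Fourth subject, cohort 3 onward.* Subjects 1-3 give 2/3 in a missed order, and the subject without a DLT is still inside the 28-day window, so the SRC review is not yet due. Risk is 0.51-0.71 at 120-1000 mg.
- *Replacement.* Subjects 1 and 3 have DLTs and subject 2 is not evaluable. The evaluable data are 2/2, fewer than three, so Section 3.4 directs a replacement. Risk is 0.65, 0.89 and 0.86 at 120, 360 and 1000 mg.
- *Expansion approved after one DLT.* The entry points are admissible: 1/3 at 14 mg 0.21, 1/2 at 40 mg 0.205, 1/3 at 120 mg 0.17. If the next subject has a DLT, the data become 2/4 at 14 mg (0.50), 2/3 at 40 mg (0.47) or 2/4 at 120 mg (0.40). At 40 mg, one DLT-free subject before the second DLT gives 2/4 (0.36).
- *2/4 at 360 and 1000 mg.* There is almost no route. The fourth place is used, four evaluable subjects need no replacement, and 1/3 at these doses (0.28 and 0.275) would not have been admissible for expansion.

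**Step 4: sensitivity to history.** At 40 mg after 0/6 at 14 mg, 2/3 is 0.247 and 2/4 is 0.183. Over all allowed sizes of DLT-free lower cohorts, 2/3 stays above 0.25 at 14, 120, 360 and 1000 mg and in 4 of 5 histories at 40 mg. For 2/4 the count at 40 mg is 3 of 5.

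At 720 mg after 0/6 at 480 mg (Protocol 1.6), the lower-dose DLT data are not in the documents. Five assumed DLT-free histories, from none to 0/6 at each of 14, 40, 120 and 360 mg, give 0.26-0.375 at 2/3 and 0.18-0.29 at 2/4. These five do not bound the answer: 0/2, 0/2, 0/3 and 0/6 at those doses gives 0.24 and 0.17 by the same calculation.

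**Step 5: how often the pattern arises.** For true DLT rate p, the rule fires with probability p². Exactly two DLTs among subjects 1-3 in a missed order has probability 2p²(1−p). At Table 20's rates for 360 mg:

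- p = 0.342: 0.117 fires; 2 × 0.117 × 0.658 = 0.154 missed.
- p = 0.45: 0.203 fires; 2 × 0.2025 × 0.55 = 0.223 missed.

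These are frequencies of the DLT pattern, not of an extra subject being dosed. The latter also needs an available route and DLTs known in time, and the documents give no DLT timing.

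**The case against.** The strongest reply is that the early rule covers the first two subjects because other controls cover the rest. Two related Grade 4 DLTs, or any Grade 5 event, suspend accrual in every order. From cohort 3 onward, three evaluable subjects bring the SRC and BLRM review. Going beyond four subjects needs an SRC decision. DLTs are reported as SAEs within 24 hours (8.1.4, 8.2), the medical monitor confirms eligibility (3.3), and a communication plan shares safety data (3.4). This stands and narrows the point: a reader might infer that two DLTs in another order never stop enrollment, and that is not so.

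The review at three evaluable subjects does not close the gap. It waits until every subject who has started treatment finishes 28 days or has a DLT, replacements come before it, and an expansion decision precedes the second DLT. The suspension rule leaves out pairs that include a Grade 3 DLT, and Table 3 lists many Grade 3 DLTs.

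Two further objections stand. The SRC charter, which holds the decision process, is not available and may impose conditions on an expansion. The 360 mg rates in Step 5 also sit poorly with 0/6 at 480 mg, which has probability of at most 0.658⁶ = 0.08 or 0.55⁶ = 0.03 if the rate at 480 mg is no lower.

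A reader might also infer that EWOC is breached. It is not: its wording governs the choice of dose for the next cohort.

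**Conclusion.** The gap is real but narrow. For two DLTs at an uncleared dose, at least one below Grade 4 and not in the first two subjects, the protocol text requires no stop or re-run before a fourth subject, a replacement, or later subjects of an approved expansion. With minimum-size DLT-free lower cohorts, overdose risk is 0.47-0.71 at 2/3 (14-1000 mg) and 0.36-0.50 at 2/4 on the expansion route (14-120 mg), against 0.25.

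The documents do not support saying that the limit is exceeded at every dose and history: larger lower cohorts at 40 mg bring it below 0.25, and the 720 mg values lie around the limit. The finding rests on the protocol text without the SRC charter and on the plan's prior, which reproduces Table 19. With six cohorts up to 480 mg enrolled and 720 mg open by the October 2021 cutoff, the practical effect is limited. It rates as a cheap improvement.

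**What to change.** In Section 3.5, replace the condition on the first two consecutive subjects with any two subjects at a dose level not yet cleared, and state that fourth, replacement and expansion subjects count. Keep the same stop, BLRM re-run and SRC decision. It would help to show the SRC the result with and without pending DLT-free subjects.

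The cost is one phrase, plus one model run and one SRC contact when a second DLT occurs. Some open cohorts will pause, including paths that would later be admissible: at 120 mg, 2/4 is 0.40 but 2/6 is 0.22. The SRC can still choose to stay at the dose, so such a path is delayed and not closed. At 14 mg the fallback of 7 mg also fails after 2/3 (0.54) and 2/4 (0.38), but the present rule already has that consequence after 2/2 (7 mg 0.74).

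A binding check after a single DLT is not advised. After 1/1 at 14 mg, neither 14 mg (0.51) nor 7 mg (0.44) would be admissible, whereas 1/3 at 14 mg is (0.21).

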3.6 Safety Review Committee

The SRC will consist of the Sponsor's medical representative and the Principal Investigator or delegate from each active study center. The SRC will be co-chaired by 1 of the participating Principal Investigators and the Sponsor's medical representative. The study statistician will participate in the SRC. *Ad hoc* participants such as the clinical pharmacology scientist and clinical operations leader may be invited as appropriate. Additional experts may be consulted by the SRC as needed. Appropriate representatives of the coordinating contract research organization will also attend and minute the meeting.

The SRC has the responsibility for monitoring the clinical study's progress and the safety of the participating subjects. After there are 2 evaluable subjects for the first 2 cohorts and at least 3 evaluable subjects for subsequent cohorts at each dose level during Phase 1 of the study, the SRC will review and assess all available safety data from the cohort together with available PK data and recommendations from the BLRM to make a decision on the dose for the next cohort of subjects. The decision may be to:

- Proceed with dose escalation;
- Expand the cohort to a maximum of 6 evaluable subjects;
- De-escalate the dose to a lower dose level or to an intermediate lower dose level; or
- Stop the dose escalation.

The decisions and decision-making of the SRC will be documented and will be provided to the Investigators before dosing any new subjects on the next dose level.

During the dose expansion phase (Phase 2a) of the study, an Independent Data Monitoring Committee (IDMC) will periodically review all safety data generated throughout the dose expansion phase (Phase 2a) part of the study on a regular basis ([Section 3.7](#)).

All details regarding the SRC composition, meetings, reviewed data and the decision-making process will be documented in the study-specific SRC Charter.

3.7 Independent Data Monitoring Committee

Prior to initiation of dose expansion phase (Phase 2a), an Independent Data Monitoring Committee (IDMC) will be established consisting of clinical experts who are not directly involved in this clinical study. The IDMC will review all safety data generated throughout the dose expansion phase (Phase 2a) part of the study on a regular basis. Based on the outcome of their review, the IDMC will provide recommendations to the Sponsor with regard to study conduct or study procedures. The set-up and operational process for this IDMC will be described in a separate IDMC charter.

3.8 Dose Expansion Phase (Phase 2a)

Once at least one RP2D dose has been determined, then enrollment into 1 or more expansion cohorts for selected cancer indication in the dose expansion phase (Phase 2a) will begin. Other expansion cohorts may follow with the same or a different RP2D dose level. An optimum Simons two-stage design will be applied for the preliminary efficacy analyses for the following expansion cohorts ([Figure 2](#)):

- Expansion Cohort A will enroll up to a total of 39 subjects with microsatellite stable CRC with rat sarcoma gene (RAS) wild-type tumor, the interim analysis (IA) will be conducted after 11 subjects.
- According to Simons two-stage design it was planned that Expansion Cohort B will enroll up to a total of 41 subjects with ccRCC, and the IA will be conducted after 15 subjects. After conducting the interim analysis for Cohort A and C and stopping these cohorts for futility, it was considered unlikely that the continuation criteria can be met in Cohort B. Hence it was decided to prematurely stop enrollment after 8 patients in Cohort B.
- Expansion Cohort C will enroll up to a total of 41 subjects with advanced or metastatic NSCLC with an EGFR mutation, the IA will be conducted after 15 subjects.

